6 MANAGEMENT OF TOXICITY AND TREATMENT DISCONTINUATION

6.1 General Management

Vital signs (blood pressure, respiratory rate, pulse and temperature) and inspection of injection sites will be monitored at 0-5 minutes, at 15-30 minutes, and then at 2 hour (\pm 30 minutes) after each injection of investigational drug.

For cohort in dose escalation phase, the first three subjects should be hospitalized following first dose of the investigational drug injection, vital signs and inspection of injection sites will be monitored after injection of investigational drug for following time point: at 0-5 minutes, at 15-30 minutes, at 2 hour (\pm 30 minutes), at 4 hour (\pm 30 minutes), at 6 hour (\pm 30 minutes), before bed and before discharge.

6.2 Management of Drug-Induced Toxicities

Risks to the patients will be mitigated with careful clinical monitoring and evaluation of laboratory safety parameters.

The most likely adverse effects anticipated in this study are local skin reaction at the injection site, fever, chills and sweats as a direct effect of active immunotherapy. These adverse effects seldom require therapy; but anti-pruritics may be used only if symptomatic. If necessary, NSAIDs may be used to control fever and pain, but steroids are prohibited. Pre-medication with anti-pruritics or steroids is prohibited. The study treatment will continue despite these symptoms.

Slight to moderate dermal edema and erythema were observed in animal studies although these were not considered adverse effects. Investigators should treat these conditions per their normal practice. Subjects will be instructed to notify the Investigator if they experience drainage of fluid, injection-site reaction with break in skin and blue-black discoloration and swelling.

Less common but more severe allergic reactions include severe bronchospasm and anaphylaxis. In the presence of these conditions, treatment should be immediately discontinued and the subject treated with epinephrine, steroids, oxygen, volume support, or other bronchodilators and supportive care as needed. The study treatment will be discontinued and the subject will be continuously monitored and may be withdrawn from the study.

Autoimmune disorder may occur since low level of Globo H is expressed by epithelial cells. However, the likelihood of autoimmune disorder is rare since Globo H expression is confined to the apical epithelial cells at lumen borders, a site which appears not to be accessible to the immune system. Immune complex disease as manifested by skin, joint, renal or other changes could occur, but these should be rare in the absence of prior exposure to Globo H.

Treatment will be discontinued, if there is evidence of frequent toxicities associated with severe epithelial cell injury. If any SAE's require the use of immunosuppressive therapies (e.g., cyclosporin, rapamycin, tacrolimus, rituximab, alemzutumab, natalizumab, iv/oral steroid, etc.) or immunomodulatory therapies (e.g., plasmapheresis, intravenous immunoglobulins), then the subject should be terminated from the treatment, and continue to be followed up until disease progression, early termination or end of study.

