6.3 Definition and Management of Dose Limiting Toxicity

- An event in dose escalation phase will be considered a dose limiting toxicity (DLT) if it occurs within the first 6 weeks after the administration of OBI-833/OBI-821 and meets the following criteria:
 - Any Grade 3 or Grade 4 toxicities considered at least possibly related to the investigational drug.
- Any subject who develops a DLT will be terminated from study treatment.
- All subjects who have a Grade 3 or 4 clinical or laboratory abnormality at the time of withdrawal from the study must be followed until resolution to Grade 2 or less, unless it is unlikely to improve because of underlying disease.
- If there is any subject of the first 3 or there is more than 1 subject of the first 6 who develop DLT, then the dose escalation will be suspended until a full review by the Data and Safety Monitoring Board. Dose modification, such as a 50% dose reduction for the next dose cohort, may be considered, as justified by emerging safety data. If dose reduction is required for the subjects in cohort 1 (10 µg Cohort), study will be suspended temporally. Data and Safety Monitoring Board will review the emerging safety data and instruct if the study can be resumed and continue to enroll Cohort 1 subject without dose reduction.

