11 CRITERIA FOR REMOVAL FROM PROTOCOL THERAPY AND OFF STUDY CRITERIA

11.1 Criteria for Removal from Protocol Therapy

Subjects will be discontinued from the study treatment with the investigational drug for any of the following reasons:

- Evidence of disease progression based on RECIST 1.1 Criteria (see Section 10) in dose escalation phase.
- Noncompliance.
- Subject voluntarily withdrew his/her consent.
- Subject develops a DLT.

- Extraordinary medical circumstances: Subject who, in the opinion of the Investigator, should be discontinued for their well-being or if at any time the treatments prescribed by this protocol are detrimental to the subject's health, the subject may be withdrawn from the study (see Section 5). In this event, reasons for withdrawal should be clearly documented.
- If subject becomes pregnant or requires breast-feeding during the Treatment period.
- Subjects who are off protocol therapy instead of disease progression will need to complete End of Study Visit.
- All surviving subjects will be followed up for survival status by phone contact or subjects' clinic visit every 12 weeks for up to 24 weeks.

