13.1 Adverse Events

Based on ICH guidelines, an adverse event (AE) is defined as any untoward medical occurrence in a clinical study subject administered a medicinal product. An AE does not necessarily have a causal relationship with the treatment. An AE can therefore be any unfavorable and unintended sign (including an abnormal finding), symptom, or disease temporally associated with the use of a medicinal product, whether or not related to the investigational drug. This includes any occurrence that is new in onset or aggravated in severity or frequency from the baseline condition, or abnormal results of diagnostic procedures, including laboratory test abnormalities.

Treatment-Related AEs

A treatment-related AE is an event that is considered associated with the use of a study treatment (OBI-833/OBI-821) if the attribution is possibly, probably, or definitely related by the definitions listed in Section 13.3.

Adverse events (AEs) and toxicities will be assessed throughout the study and graded according to US NCI Common Toxicity Criteria, Version 4.0, developed by the Cancer Therapy Evaluation Program at the National Cancer Institute. The criteria for unacceptable toxicities should include any \geq Grade 4 toxicity, with the exception of local skin reactions, fever, chilling, sweats, urticaria, and/or pruritis since these are common side effects of antibody/adjuvant administration, are reversible, and controlled by supportive management. Theoretically, immune complex disease as manifested by skin, joint, renal, or other manifestations could occur, but these should be rare in the absence of prior exposure to mouse protein. These will be an indication to stop therapy in the affected subjects, but accrual of new subjects may continue.

In general, Grade 1 (Mild) and Grade 2 (Moderate) adverse events are considered acceptable. Grade 3 AEs are Severe but reversible or medically manageable conditions involving major organ and organ function. Grade 4 AEs are Life-threatening consequences; urgent intervention indicated.

Any adverse event must be recorded in the subject medical records and on the eCRFs. The onset and end dates, severity, duration, effect on investigational drug administration (e.g., discontinuation), relationship to investigational drug, and administration of any other drug(s) for treatment of AEs will be recorded for each adverse event.

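### For a related Grade 3–4 injection-site reaction, fever, chills or sweats, Protocol 6.2 says treatment continues while 6.3 and 11.1 end it, and 13.1 adds a third, unlinked standard

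*Protocol*

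**What the plan says.** Section 6.2 lists what the sponsor expects: "The most likely adverse effects anticipated in this study are local skin reaction at the injection site, fever, chills and sweats". It attributes these to the immunotherapy itself, allows symptomatic treatment, and concludes: "The study treatment will continue despite these symptoms". No grade is given above which this ceases to apply.

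Section 6.3 defines a DLT, for the escalation phase, as an event for which "it occurs within the first 6 weeks after the administration of OBI-833/OBI-821" and which meets one criterion: "Any Grade 3 or Grade 4 toxicities considered at least possibly related to the investigational drug". No type of event is excepted, and the synopsis gives the same definition. The consequence is "Any subject who develops a DLT will be terminated from study treatment". Section 11.1 repeats it by listing "Subject develops a DLT" among the reasons for removal from therapy.

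Section 13.1 sets a different category. "The criteria for unacceptable toxicities should include any" toxicity of Grade 4 or above, "with the exception of local skin reactions, fever, chilling, sweats, urticaria, and/or pruritis since these are common side effects". It does not mention DLT and does not refer to 6.2 or 6.3. The same section describes Grade 4 events as life-threatening.

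Two further texts are not limited to the escalation phase. Section 6.4 requires discontinuation for a list of serious events that ends with any other potentially life-threatening or disabling event which the investigator and medical monitor attribute to the study drug. Section 4.1 and the synopsis end expansion-phase treatment for intolerable toxicity.

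**The concern.** The reactions handled inconsistently are the ones the protocol expects most. Because 6.2 calls them a direct effect of the immunotherapy, a Grade 3 or 4 case would normally be judged at least possibly related and so meet the causality condition in 6.3. For that event in the first 6 weeks of escalation, an investigator following 6.2 gives the next dose and one following 6.3 and 11.1 stops. Both instructions cannot be met, and no section says which takes precedence.

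The statistical stake is comparability. Adverse events leading to discontinuation are a planned summary (12.5.1), exposure is summarised (12.5.3), and DLTs drive escalation (4.1). Two subjects with the same event can therefore contribute differently to the discontinuation tally and to later exposure. In the expansion phase there is no DLT rule to settle the matter, and 6.2 and 13.1 point one way while 6.4 and the intolerable-toxicity stop point the other.

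**Working it through.** **The plan's own figures.** Three cohorts × 6 = 18 in escalation, and 18 + 14 = 32 in total. Both match section 12.2. The protocol states no DLT rate, tests no hypothesis (12.1) and does not base its size on statistics (12.2), so there is no operating characteristic to reproduce.

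**One event followed through the sections.** Take an injection-site reaction judged possibly related, in week 3.

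| Section | Grade 3, escalation | Grade 4, escalation | Grade 4, expansion |
|---|---|---|---|
| 6.2 | continue | continue | continue |
| 6.3, synopsis, 11.1 | DLT, end treatment | DLT, end treatment | DLT not applicable |
| 13.1 | below the Grade 4 threshold | exempt from unacceptable toxicity | exempt from unacceptable toxicity |
| 6.4 | depends on judgement | discontinue if judged potentially life-threatening or disabling and attributable | same |
| 4.1 (intolerable toxicity) | not stated for this phase | not stated for this phase | stop if intolerable |

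The first two rows contradict each other in both escalation columns. In the expansion column, 6.2 and 13.1 pull against 6.4 and 4.1, since 13.1 itself calls Grade 4 life-threatening.

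**Does the 3+3 count change?** Not on the literal text. The count in 4.1 uses DLTs, DLT is defined once, and 6.2 and 13.1 contain no counting rule. It changes only if 6.2 or 13.1 is taken as an implied exception.

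**Size if an exception is read in.** Let p be the chance per subject of a related Grade 3–4 reaction of this kind in 6 weeks. This is an assumption; the range used is 5%, 10% and 20%. Under 4.1 a cohort passes on 0 of 3, or on 1 of 3 followed by 0 of 3:

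P(pass) = (1−p)³ + 3p(1−p)² × (1−p)³ = (1−p)³ + 3p(1−p)⁵

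- p = 5%: 0.857 + 0.116 = 0.973, so 2.7% are stopped
- p = 10%: 0.729 + 0.177 = 0.906, so 9.4% are stopped
- p = 20%: 0.512 + 0.197 = 0.709, so 29.1% are stopped

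If the reactions are not counted and there are no other DLTs, every cohort passes, so these are the chances that the two readings give different outcomes at one dose. The plain binomial chance of 2 or more in 6 (3.3%, 11.4%, 34.5%) is too high, because the second three subjects are enrolled only after exactly one DLT in the first three.

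Adding an assumed 5% rate of other DLTs, the total rate is 1 − 0.95(1−p), that is 9.75%, 14.5% and 24%. P(pass) is 0.973 if the reactions are not counted, and 0.910, 0.824 and 0.622 if they are.

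These figures use the rule in 4.1. Section 6.3 words suspension differently, on any DLT in the first three. That is a separate discrepancy; under that wording the chance of a suspension from these reactions alone is 1−(1−p)³ = 14.3%, 27.1% and 48.8%.

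**The case against.** The strongest reply is that context limits 6.2. It says these effects seldom need therapy, and 13.2 describes earlier experience as generally mild to moderate. On that reading 6.2 covers expected low-grade symptoms and 6.3 governs Grades 3 and 4. The reading is plausible, but 6.2 does not state it and 13.1 shows that the authors considered these same reactions at Grade 4 and above. The text conflict therefore stands.

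Other parts of the reply succeed and limit the point.

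- A reader might infer that 13.1 exempts these reactions from being DLTs. It does not. Its exception applies only to unacceptable toxicity at Grade 4 or above, and it sets no rule for Grade 3 reactions. Nor does it say plainly what follows from the category.
- A reader might infer that the primary safety endpoint and the 3+3 count turn on which section a site follows. Section 9.1 defines the endpoint by adverse events, laboratory values, vital signs and physical examination, without naming DLT, and 12.5.1 tabulates events by grade and relationship. The event is reported whichever section is followed. The count rests on one definition, and the DSMB assists with escalation decisions.
- A reader might infer that in expansion nothing stops treatment for such a reaction, even at Grade 4. Section 6.4, the intolerable-toxicity stop, the 6.2 rule on serious events needing immunosuppression, and the well-being clause in 11.1 all can. The fault is that they are not reconciled with 6.2 and 13.1.

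Finally, this version says that the escalation data have been reviewed and an expansion dose recommended. New wording cannot alter those escalation steps.

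**Conclusion.** The contradiction is real and in the current text. For a related Grade 3–4 injection-site reaction, fever, chills or sweats within 6 weeks in escalation, 6.2 continues treatment and 6.3, the synopsis and 11.1 end it. Section 13.1 adds a differently graded standard with no link to either. In expansion, 6.2 and 13.1 are unreconciled with 6.4 and 4.1.

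The consequence is limited. Adverse event recording is unaffected. Discontinuations and later exposure can differ for identical events. The DLT count is affected only through an unwritten exception; if one were applied, the two readings would differ on escalation at one dose with probability 2.7%, 9.4% or 29.1%. Those figures assume reaction rates of 5%, 10% and 20%, independent subjects, no other DLTs and the 4.1 rule. The protocol supports none of these rates in particular, and the effect is nil if no such reaction reaches Grade 3. What remains open is how escalation DLTs and discontinuations are reported, and which stopping text applies in expansion. It should be corrected; it does not undermine the design.

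**What to change.** Reconcile 6.2, 6.3, 11.1 and 13.1 with each other, and with 4.1, 6.4 and the matching synopsis text, into one rule. It should state, by grade and by phase, whether injection-site reactions, fever, chills, sweats, urticaria and pruritus count as DLTs and whether treatment stops, and the other sections should refer to it. What the rule should be is a clinical choice for the sponsor and the DSMB.

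In the report, give the escalation-phase DLT counts and discontinuations with and without these reactions, so that the dose conclusion can be read either way.

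The cost is amendment wording and one extra line in a table. No new data are needed.

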6.3 Definition and Management of Dose Limiting Toxicity

- An event in dose escalation phase will be considered a dose limiting toxicity (DLT) if it occurs within the first 6 weeks after the administration of OBI-833/OBI-821 and meets the following criteria:
 - Any Grade 3 or Grade 4 toxicities considered at least possibly related to the investigational drug.
- Any subject who develops a DLT will be terminated from study treatment.
- All subjects who have a Grade 3 or 4 clinical or laboratory abnormality at the time of withdrawal from the study must be followed until resolution to Grade 2 or less, unless it is unlikely to improve because of underlying disease.
- If there is any subject of the first 3 or there is more than 1 subject of the first 6 who develop DLT, then the dose escalation will be suspended until a full review by the Data and Safety Monitoring Board. Dose modification, such as a 50% dose reduction for the next dose cohort, may be considered, as justified by emerging safety data. If dose reduction is required for the subjects in cohort 1 (10 µg Cohort), study will be suspended temporally. Data and Safety Monitoring Board will review the emerging safety data and instruct if the study can be resumed and continue to enroll Cohort 1 subject without dose reduction.

6.4 Guidelines for Individual Subject Study Treatment (OBI-833/OBI-821) Discontinuation

- In the event of a ≥ Grade 3 immune-associated AE or emergent SAE as listed below, the subject is required to discontinue study drug treatment. The Data and Safety Monitoring Board will be notified of these events and safety reporting to the various health authorities will follow each country's respective health agency guidelines.
 - Auto-immune diseases included but not limited to severe Guillain-Barré Syndrome (GBS) or chronic inflammatory demyelinating polyneuropathy (CIDP).
 - Encephalopathy or any other significant CNS involvement.
 - Anaphylaxis or respiratory failure requiring intubation and/or ventilator support.
 - Indication for emergency intervention and life-threatening consequences such as malignant hypertension, shock leading to vital organ impairment, severe cardiac arrhythmias, etc.
 - Vasculitis leading to severe ischemia and vascular neuropathy.
 - Nephritis leading to severe renal impairment.
 - Hepatitis leading to severe hepatic dysfunction.
 - Adrenal insufficiency life threatening adrenal crisis.
 - Severe pancreatitis.
 - Thyroiditis leading to \geq grade 4 hyperthyroidism or hypothyroidism.
 - Autoimmune hemolytic anemia.
 - And any other potential life threatening or disabling adverse events attributable to the study drug in the opinion of the Investigator and medical monitor.
- Immune related AEs that would NOT be considered emergent or serious, and may NOT require study treatment discontinuation may include:

- Inflammation that can be attributable to a local antitumor reaction at tumor sites or in draining lymph nodes. This includes inflammatory reactions at sites of tumor resections or exposed to radiation therapy.
- If toxicity occurs regardless of investigational drug administration that does not meet study treatment discontinuation criteria:
 - The investigational drug administration may be delayed for up to 2 consecutive weeks.
 - In the event that the administration of the investigational drug is delayed for more than 2 consecutive weeks, then the Investigator should confer with the Sponsor's Medical Monitor to discuss the appropriateness of continued treatment.
- All subjects in both phases who discontinue study treatment prematurely should undergo the early termination procedures as described in Section 5.7.
- A Data and Safety Monitoring Board will be established to assist Sponsor in monitoring the subject safety, risk/benefit, dose escalation, dose reduction and termination of the study.

7 TREATMENTS PERMITTED AND PROHIBITED DURING STUDY

7.1 **Permitted Treatments during Study**

[Dose Escalation Phase]

- 1. Analgesics: Non-steroidal anti-inflammatory drugs (NSAID), analgesics other than NSAID (like aspirin), and opiates may be used for pain control.
- 2. GCSF and Hematopoietic growth factors will be allowed in the dose escalation phase if deemed necessary by physicians.
- 3. Antihistamine (H1 and H2) and decongestant: cetirizine HCl, fexofenadine HCl, levocetirizine, and pseudoephedrine.
- 4. Antiemetic and anti-pruritics therapy.
- 5. Therapy with bisphosphonates (e.g., to treat bone metastases), is at the discretion of the investigator.

[Cohort Expansion Phase]

- 1. Analgesics: Non-steroidal anti-inflammatory drugs (NSAID), analgesics other than NSAID (like aspirin), and opiates may be used for pain control.
- 2. Antihistamine (H1 and H2) and decongestant: diphenhydramine, hydroxyzine, cimetidine, ranitidine, famotidine, cetirizine HCl, fexofenadine HCl, levocetirizine, and pseudoephedrine.
- 3. Antiemetic (eg., ondansetron) and anti-pruritics (eg., diphenhydramine or hydroxyzine) therapy.
- 4. Therapy with bisphosphonates (e.g., to treat bone metastases), is at the discretion of the investigator.
- 5. EGFR/ALK TKIs (e.g., gefitinib, erlotinib, afatinib and crizotinib), EGFR mAb (Necitumumab), bevacizumab and PD-1/PD-L1 inhibitors (e.g., pembrolizumab and nivolumab)

7.2 **Prohibited Treatments during Study**

The following treatments are prohibited during the Treatment and Post-treatment periods of the study until End of Study (Appendix II):

[Dose Escalation Phase]

- 1. Anti-cancer treatment: no other anti-cancer therapy is allowed during the study. The list of other chemotherapy agents, chemotherapeutic agents, active or passive immunotherapy, includes, but is not limited to:
 - Chemotherapeutic agents: antimetabolites, alkylating agents, vinca alkaloid, epipodophyllotoxins, taxanes, camptothecins, antitumor antibiotics, nitrosoureas folate analogue metabolic inhibitor, and miscellaneous cytotoxic agents.
 - Surgery
 - Radiotherapy
- 2. Biologic Agents: Monoclonal antibodies, Interferons and Interleukins
- 3. Immunotherapy: cyclosporin, rapamycin, tacrolimus, rituximab, alemtuzumab, natalizumab etc.
- 4. Steroids: iv/oral steroids except single prophylactic use in CT/MRI scan or other one-time use in approved indications. The interval between iv/oral steroids administration and first dose of OBI-833/OBI-821 must be more than pharmacological duration or 5 half-lives of administered steroids whichever is the longer.
 - Uses of inhaled and topical steroids are allowed.
- 5. Tyrosine kinase inhibitors
- 6. Alternative and complementary medicine may affect immune system
- 7. Other investigational drugs

[Cohort Expansion Phase]

- 1. Anti-cancer treatment: The list of chemotherapy agents, active or passive immunotherapy (Appendix II), includes, but is not limited to:
 - Chemotherapeutic agents: antimetabolites, alkylating agents, vinca alkaloid, epipodophyllotoxins, taxanes, camptothecins, antitumor antibiotics, nitrosoureas folate analogue metabolic inhibitor, and miscellaneous cytotoxic agents. EGFR/ALK TKIs are permitted.
 - Surgery
 - Radiotherapy
- 2. Biologic Agents: Interferons, Interleukins, Denosumab (RANKL inhibitor), GCSF and Hematopoietic growth factors
- 3. Immunotherapy: cyclosporin, rapamycin, tacrolimus, rituximab, alemtuzumab, natalizumab, cyclophosphamide, etc (except PD-1/PD-L1 antagonists).
- 4. Steroids: iv/oral steroids except single prophylactic use in CT/MRI scan or other one-time use in approved indications. The interval between iv/oral steroids administration and first dose of OBI-833/OBI-821 must be more than pharmacological duration or 5 half-lives of administered steroids whichever is the longer.
 - Topical (except injection sites) and inhaled steroid use is allowed

- 5. Alternative and complementary medicine may affect immune system.
- 6. Other investigational drugs

7. Subjects who continuous treatment after disease progression are allowed to concomitant use of all approved anti-cancer therapies

